APPENDIX C OVERVIEW OF RECRUITMENT PLAN (Primary Study)

The text now presented in Appendix C has been *moved* (from Section 4.0) but it has not been altered.

APPENDIX D Additional Information Regarding Primary Study Visits

The text now presented in Appendix D has been *moved* (from Section 3.0) but it has not been altered.

APPENDIX EAdditional Information Regarding LRTI Surveillance,including Active Surveillance Contact Schedule (Primary Study)

The text now presented in Appendix E has been *moved* (from Section 3.0) and minor alterations have been made. The alterations are presented below.

ACTIVE SURVEILLANCE CONTACT SCHEDULE to identify any potential LRTI case

Active surveillance is aimed at confirming that a case is/was not missed due to lack of reporting by parent(s)/LAR(s) and to remind parent(s)/LAR(s) to report cases of RTI symptoms as soon as possible themselves. Although active surveillance is an important aspect to ensure that all cases are identified timely, the number of active surveillance contacts should not be too high. Too many active surveillance contacts could put an unnecessary demand on the parent(s)/LAR(s) of the subjects and has been known to negatively impact long term compliance. In order to reduce the number of active surveillance surveillance contacts to an acceptable and valuable level, the following measures should be applied.

Active surveillance is allowed to occur through various media (e.g. text messaging, email and, telephone, and in-person) based on local possibilities

DISCONTINUATION OF ACTIVE SURVEILLANCE

Active surveillance should be suspended after there has been no contact for more than 3 planned contacts and/or no contact for more than 2 months and a final attempt has been made by mail or a live visit. If the parent(s)/LAR(s) of the subject contact the investigator/study staff at a later point in time through passive surveillance, the case should be followed up, data should be collected at intermittent period and active surveillance could be reinitiated. These subjects will however no longer be included in the ATP cohort, therefore, all efforts should be made to avoid this.

Protocol Amendment 3 Sponsor Signatory Approval

eTrack study number and Abbreviated Title	200150 (EPI-RSV-005 BOD)
Date of Amendment	Amendment 3 Final: 15 December 2017

HIV	Human Immunodeficiency Virus		
ICF	Informed Consent Form		
ICH	International Conference on Harmonization		
IEC	Independent Ethics Committee		
ILI	Influenza-like Illness		
IRB	Institutional Review Board		
IU/ml	International units per milliliter		
LAR	Legally Acceptable Representative		
LL	Lower Limit of the confidence interval		
LLOQ	Lower Limit Of Quantification		
LRTI	Lower Respiratory Tract Infection		
MedDRA	Medical Dictionary for Regulatory Activities		
mL	Milliliter		
N.A.	Not Applicable		
NH	Northern Hemisphere		
NPV	Negative Predictive Value		
OTC	Over-The-Counter		
Р	Percentile		
PCR	Polymerase Chain Reaction		

200150 (EPI-RSV-005 BOD) Statistical Analysis Plan Amendment 1 Final

PD	Protocol Deviation
PPS	Per Protocol Set
PPV	Positive Predictive Value
RDE	Remote Data Entry
RR	Respiratory Rate
RSV	Respiratory Syncytial Virus
RTI	Respiratory Tract Infection
RT- qPCR	Reverse transcription-quantitative real time polymerase chain reaction
RVP	Respiratory Viral Panel
SAE	Serious Adverse Events
SaO2	Blood Oxygen Saturation
SAP	Statistical Analysis Plan
SBIR	Randomization System on Internet
SD	Standard Deviation
SDV	Source Document Verification
SH	Southern Hemisphere
SPM	Study Procedure Manual
SR	Study Report
TFL	Tables Figures and Listings
TN	True Positive
TOC	Table of Content
ТР	True Negative
UL	Upper Limit of the confidence interval
URTI	Upper Respiratory Tract Infection
US	United States
WHO	World Health Organisation

1. DOCUMENT HISTORY

Date	Description	Protocol Version
17-JUL-2015	First version	Amendment 2 Final - 06-JUL-2016
18-MAY-2018	Amendment 1	Amendment 3 Final - 15-DEC-2017

2. STUDY DESIGN

2.1. Design summary

In the primary study, subjects were to be followed-up from birth up to the age of 2 years for RSV LRTI. Episodes of wheeze and diagnoses of asthma were also documented.

Figure 1 Study design diagram for the primary study (from birth up to the age of 2 years for detection of RSV LRTI)

V = Visit; D = Day; M = Month

ICF = Informed Consent Form; CBS = Cord Blood Sample; NS = Nasal Swab; DC = Diary Card; BS = Blood Sample ¹ An examination visit (off-site/site) is to occur for new or worsened, potential LRTI case as identified during active or passive follow-up contact. The examination visit needs to occur as soon as possible and no later than 72 hours after the potential LRTI was identified during a follow-up contact. Each subject may have none, single or multiple examination visits over the course of the study.

² A sub-cohort of subjects will be randomized for a single blood draw to occur at one of the six possible time points and will have a Visit 3 corresponding to this time point (if still participating at that time); either V3a at 2, V3b at 4, V3c at 6, V3d at 12, V3e at 18 or V3f at 24 months.

* All follow up procedures associated with V2 (e.g. ICF) must be performed within 5 working days after birth.

200150 (EPI-RSV-005 BOD)

Statistical Analysis Plan Amendment 1 Final

- Type of design: Prospective, epidemiological, interventional, multi-country, cohort study.
- Study population:
 - A cohort of approximately 2400 infants will be included in the study at birth and followed-up up to 2 years of age.
 - A sub-cohort of subject will be randomized for a single blood draw to one of the time point at 2, 4, 6, 12, 18 or 24 months of age as described in Table 1.

Table 1Blood sample collection

Time point	Seroprevalence sub-cohort Number of allocated subjects*
2 months	200
4 months	200
6 months	250
12 months	300
18 months	450
24 months	600
Total	2000

Note: Only one blood sample will be withdrawn from each subject in this sub-cohort.

*Number of subjects selected per time point is calculated based on the required number of subjects for adequate analysis considering an accumulating drop-out of subjects. Actual numbers might be less due to drop-outs and exclusion of subjects with gestational age <36 weeks..

- Type of study: Self-contained.
- Data collection: Electronic case report form (eCRF).
- Biological samples (Primary Study only):
 - Cord Blood collected from all participating subjects, at birth.
 - Nasal swabs collected from subjects with potential LRTI.
 - Serum collected from a sub-cohort of subjects, excluding those born at a gestational age of less than 36 weeks. Sampling time points for this sub-cohort will be randomly allocated as specified in Table 1.
- Duration of the study: Approximately 2 years for each participant enrolled in the primary study and an additional (approximately) 3 to 4 years for each participant enrolled in the extension study.
 - Epoch 1 (Primary Study): Begins at birth (Visit 1) and ends at the age of approximately 2 years (Visit or contact at 2 years).
 - Epoch 2 (Extension Study): Begins with the first contact for the extension study (at approximately age 2 years); ends with the contact at approximately the sixth birthday. Table 2 presents the study groups and epochs foreseen in the study.

200150 (EPI-RSV-005 BOD)

Study Groups	Number of subjects	Age (Min/Max)	Epoch 1	Epoch 2
Primary	Approximately 2400	0 days - 2 years	х	
Extension	Maximum 2400	Approximately 2 years to 6 years		х

Statistical Analysis Plan Amendment 1 FinalTable 2Study groups and epochs foreseen in the study

* Data collection will also occur from medical charts retrospectively for those who have a gap period between the end of the primary study and providing re-consent for the extension.

Surveillance Plan:

- Surveillance for RSV Lower Respiratory Tract Infection (RSV LRTI), wheeze and asthma during the Primary Study period.
- Surveillance for wheeze and asthma during the extension study period.
- Safety Follow-up:
- Study procedure related Serious Adverse Events (SAEs) to be reported throughout the study.

This comprehensive analysis has been structured according to the endpoints per protocol. The table below summarises for the reader where analyses are presented. Full details of endpoints are given in section 4.

Table 3Analyses topics summary

Analysis	Endpoint	Endpoints listed in section	Analysis presented in section
Incidence	Co-primary	4.1	6.6.1
	Secondary	4.2	6.6.26.6.2
	Tertiary	4.3	6.6.3
Health care utilization	Co-primary	4.1	6.7
Performance of case definitions	Co-primary	4.1	6.8.1
	Tertiary	4.3	6.8.2
Neutralizing antibodies over time and protection against RSV disease	Secondary	4.2	6.9.1 6.9.2
	Tertiary	4.3	6.9.3
Other viruses and RSV infections	Tertiary	4.3	6.10
Compliance with protocol	Tertiary	4.3	6.11

Please note that the extension analyses are not described in this SAP.

Please note that the extension analyses are not described in this SAP.

2.2. Discussion of the study design

The multi-country design of both the primary and extension studies will provide robust, multinational estimates of the incidence of RSV-associated LRTI during the first two years of life and assess the amount of wheeze and asthma that may be attributable to those early RSV-LRTI infections.

2.2.1. Primary study

The Primary study will determine the incidence and associated healthcare utilization of RSV-associated LRTIs in infants from birth up to the age of 2 years, and assess the performance of a new LRTI case definition and severity scale. Using a cohort representing the general population of newborn infants, the study is designed to identify RSV-associated LRTI cases at any severity, and will not be limited to those that require hospitalization and/or other essential medical care. This will provide a comprehensive and accurate measure of the overall burden of disease, whereas many previous case-control or hospital-based cohort studies were limited to the hospitalized cases of RSV-associated LRTI.

The association of other respiratory viruses with RSV-associated LRTI and/or severe LRTI, and the impact of potential RSV risk factors on the incidence and severity of RSV-associated LRTI will also be explored. In order to assess and adjust for other potential confounders in the various analyses, data on the subjects' demography and lifestyle factors will be collected at baseline, and followed up quarterly for changes, during the regular follow-up contacts.

3. OBJECTIVES

3.1. Co-primary objectives

• To determine the total health burden* of RSV-associated RTI with a suspicion of involvement of the lower respiratory tract.

*Health burden refers to burden of the disease imposed on the study population in terms of incidence of the disease and associated healthcare utilization in any healthcare setting.

• To assess the performance of the LRTI case definition and severity scale for RSV associated cases.

3.2. Secondary objectives

In a cohort of infants followed-up from birth up to 2 years of age;

- To determine the total health burden of non-RSV-associated RTI with a suspicion of involvement of the lower respiratory tract.
- To evaluate the association between RSV-associated LRTI, RSV-associated severe LRTI and RSV neutralizing antibodies in the baseline cord blood samples collected from subjects, at birth.
- To determine the prevalence of RSV infection, at 2, 4, 6, 12, 18 and 24 months in a randomly selected sub-cohort of subjects by assessing antibodies in serum.
- To assess the between calendar year variability in the incidence rates of RSV-associated LRTI.

3.3. Tertiary objectives

In a cohort of infants followed-up from birth up to 2 years of age;

- To explore the association of co-infections with the incidence of RSV-associated LRTI and/or severe LRTI (as determined by the LRTI case definition and severity scale) using xTAGTM respiratory viral panel (RVP) fast assay.
- To explore the association of RSV and other respiratory viruses with the incidence of LRTI and/or severe LRTI (as determined by the LRTI case definition and severity scale) using xTAGTM RVP Fast assay.
- To explore the association of RSV viral load with the incidence of RSV-associated RTI, LRTI and/or severe LRTI (as determined by the LRTI case definition and severity scale).
- To explore the impact of changes to the symptoms and threshold levels of symptoms in the LRTI case definition and severity scale.

200150 (EPI-RSV-005 BOD)

Statistical Analysis Plan Amendment 1 Final

- To assess the impact of potential RSV risk factors (e.g. complications at birth, family history of respiratory disease, living environment and household composition, breast feeding, passive smoking, day care attendance) on the incidence and severity of RSV-associated LRTI.
- To explore the impact of variations in cord-blood sample collection variables on the stability of test results.
- To assess the natural decay of maternal antibody levels using a single follow-up blood sample collected from a randomly selected sub-cohort of subjects at 2, 4, 6, 12, 18 and 24 months.

4. ENDPOINTS

4.1. Co-primary endpoints

- Occurrence of RSV as confirmed by RT-qPCR.
- Occurrence of different types of healthcare utilization*.

* Healthcare utilization includes primary, secondary and tertiary care settings such as self-care with OTC drugs, GP visits, ER visits, hospital visits, etc.

- Occurrence of LRTI/severe LRTI as classified by the LRTI case definition and severity scale.
- Occurrence of LRTI/severe LRTI as classified by the existing comparator LRTI case definition by WHO and by Nokes et al.

4.2. Secondary endpoints

- Levels of RSV neutralizing antibodies in the cord blood samples collected at birth.
- Levels of RSV neutralizing antibodies in the blood samples collected at 2, 4, 6, 12, 18 and 24 months.
- Occurrence of LRTI/severe LRTI cases as classified by the LRTI case definition and severity scale, in the subgroups of subjects recruited from Months 1-6 and 13-18.

4.3. Tertiary endpoints

- Occurrence of RSV and other respiratory viruses as confirmed by xTAG[™] RVP Fast assay:
 - Parainfluenza virus type 1, 2, 3, and 4
 - Human Metapneumovirus
 - Rhinovirus
 - Adenovirus
 - Bocavirus

- Coronavirus 229E, OC43, NL63, HKU1
- RSV
- Influenza A, including subtypes H1 and H3
- Influenza B
- RSV viral load as determined by RSV RT-qPCR.
- Occurrence of any symptom identified in cases of potential LRTI.
- Cord-blood sample collection variables including collection and storage times and temperatures.
- Occurrence of potential risk factors including complications at birth, family history of respiratory disease, living environment and household composition, breastfeeding, passive smoking and day-care attendance.

5. ANALYSIS SETS

5.1. Definition

5.1.1. Screened cohort

The screened cohort will include all subjects screened for the study. This cohort will include all subjects with an ICF signed before birth. All subjects who signed the ICF before birth. All the aggregated information (anonymous) for these subjects will be collected in a logbook.

5.1.2. Total enrolled cohort

The total enrolled cohort will include all subjects enrolled in the study, without ICF issues (ICF signed before birth and re-signed after birth).

5.1.3. Per-protocol Set (PPS)

Note that in order to align to ICH and cDISC terminology the According To Protocol (ATP) cohort as stated in the protocol has been renamed Per-Protocol Set (PPS) respectively.

The PPS will include all subjects meeting all elimination criteria up to the time of their censoring (study termination), either at study completion or prematurely as drop-out (e.g. withdrawn consent, lost-to-follow-up, lack of compliance).

5.1.4. Total sub-cohort

All subject randomized to a blood sampling visit and with available result for blood sampling for either RSV A or RSV B.

5.1.5. Sub-cohort in PPS

The PPS sub-cohort will include subjects for whom a blood sample result will be available (at Month 2, 4, 6, 12, 18 or 24). Analyses will be done on the PPS sub-cohort from the total cohort defined in section 5.1.2, as well as from the PPS defined in section 5.1.3.

5.2. Criteria for eliminating data from Analysis Sets

Elimination codes are used to identify subjects to be eliminated from analysis. Detail is provided below for each set.

5.2.1. Elimination from Total enrolled cohort

Code 900 (invalid informed consent or fraud data) will be used for identifying subjects eliminated from ES

5.2.2. Elimination from Per-protocol analysis Set (PPS)

5.2.2.1. Excluded subjects

A subject will be excluded from the PPS analysis under the following conditions

Code	Condition under which the code is used
900	Invalid informed consent or fraud data
200/2010	Protocol violation (inclusion/exclusion criteria)

5.2.3. Elimination from Total sub-cohort

5.2.3.1. Excluded subjects

Code	Condition under which the code is used	
900	Invalid informed consent or fraud data	
200/2010	Protocol violation (inclusion/exclusion criteria)	
2500	Subjects not randomize to a blood sampling visit	
2502	Serological results were not available for subjects at visit 3 who had a BS as randomized from SBIR	

5.2.4. Elimination from Per Protocol Set Sub-cohort (PPS Sub-cohort)

5.2.4.1. Excluded subjects

A subject will be excluded from the PPS sub-cohort analysis under the following conditions.

Code	Condition under which the code is used	
900	Invalid informed consent or fraud data	
200/2010	Protocol violation (inclusion/exclusion criteria)	
2500	Subjects not randomize to a blood sampling visit	
2501	Blood sample taken but: non-compliance with blood sampling	
	schedules	
2502	Serological results were not available for subjects at visit 3 who had a	
	BS as randomized from SBIR	

5.3. Important protocol deviation not leading to elimination from per-protocol analysis set

Not applicable.

NOV LIVIT HUSPILAIIZALIUH	Needing the case definition of KSV LK11 and 1s associated with
	nospitalization
RSV severe LRTI*	Infant with RSV LRTI AND
	At least one of the following two
	• $SnO_2 < 90\%$ AND clinical diagnosis of LRTL or
	bronchialitis
	bionchiolius
	• Lower chest wall indrawing

200150 (EPI-RSV-005 BOD) Statistical Analysis Plan Amendment 1 Final

Endpoint	Case definition		
RSV severe LRTI	Meeting the case definition of RSV severe LRTI and is		
hospitalization	associated with hospitalization		
WHO 2015			
RSV LRTI*	Infant with history of cough OR		
	Difficulty breathing ²] AND		
	[SpO ₂ < 95% OR		
	RR increase ³] AND		
	Confirmed RSV infection ⁴		
RSV LRTI hospitalization	Meeting the case definition of RSV LRTI AND		
	associated with hospitalization		
RSV severe LRTI*	Infant with RSV LRTI AND		
	[SpO ₂ < 93%, OR		
	Lower chest wall indrawing]		
RSV severe LRTI	Meeting the case definition of RSV severe-LRTI, AND		
hospitalization*	associated with hospitalization		
LRTI (all cause)	[Infant with history of cough OR		
	Difficulty breathing ²] AND		
	[SpO ₂ < 95% OR PR increase ³]		
Severe LRTT (all cause)			
	[SPO2 < 93%, OR Lower chest wall indrawing]		
Exploratory definitions			
RSV I RTI	[Infant with Couch OR		
	Difficulty breathing AND		
	$[SnO_2 < 95\% OR]$		
	RR increase OR		
	Lower chest wall indrawing] AND		
	Confirmed RSV infection ⁴		
RSV LRTI hospitalization	Meeting the case definition of RSV LRTI AND		
	associated with hospitalization		
RSV severe LRTI	Infant with RSV LRTI AND		
	SpO ₂ < 93%		
RSV severe LRTI	Meeting the case definition of RSV severe-LRTI		
hospitalization	AND		
	associated with hospitalization		
RSV very severe LRTI	Meeting the case definition of RSV LRTI AND SpO ₂ < 90%		
RSV very severe LRTI	Meeting the case definition of RSV very severe-LRTI		
hospitalization	AND		
	associated with hospitalization		

¹Surveillance mechanism not designed to detect cases meeting this endpoint.

² Based on history reported by parents/LARs and includes difficulty breathing associated with nasal obstruction

³ RR defined as ≥ 60/minute (< 2 months of age); ≥ 50/minute (2 to 11 months of age); ≥40/minute (12 to 24 months of age)

⁴RSV infection confirmed on nasal swab positive for RSV A or B by quantitative polymerase chain reaction (qPCR)

⁵RSV sampling and testing is based on medical judgment of medical practitioner or driven by algorithm

⁶Hospitalization is defined as a medical decision requiring infant admission for observation or treatment

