Runny nose, OR	Child with RTI AND	Child with LRTI AND
Blocked nose, OR	SaO2 < 95%*, OR	SaO2 < 92%*, OR
Cough	RR increase:	Difficulty breathing leading to:
	> 60/min < 2m of age	Irritability/agitation, OR
	> 50/min 2-11m of age	Lethargy/sleepiness, OR
	> 40/min 12-24m of age	Severe chest indrawing, OR
		Reduced/no vocalization, OR
		Apnoea > 20 sec, OR
		Cyanosis, OR
		Stop feeding well/dehydration

Table 4 LRTI case definition and severity scale

* Measured by oximeter. RR= Respiratory Rate; SaO2= Blood Oxygen Saturation; m = months. RTI = Respiratory Tract Infections; LRTI = Lower Respiratory Tract Infections

Case definition of LRTI and severe LRTI by Nokes et al.

LRTI is diagnosed when a child has a history of acute cough or difficulty in breathing and ≥ 1 of the following:

- Fast breathing for age (≥ 60 breaths/minimum if the child is < 2 months old or ≥ 50 breaths/minimum if the child is 2–11 months old)
- Indrawing, or
- Low oxygen saturation (< 90%) by pulse oxymetry or inability to feed (prostration or unconsciousness), when accompanied by a clinical diagnosis of LRTI or bronchiolitis.

Severe LRTI was diagnosed when a child had LRTI meeting second and/or third bullet above.

Case definition of LRTI by WHO (2015) [Modjarrad, 2016]

LRTI is diagnosed when a child <5 years presents with cough and/or difficulty in breathing has the following symptoms:

- Fast breathing, (> 60 per minute in a child < 2 months of age, > 50 per minute in a child 2 to 11 months of age and; > 40 per minute in a child 12 to 59 months of age), or
- Oxygen saturation < 95% by pulse oximetry.

Severe LRTI is diagnosed when a child has LRTI and 1 or more of the following features of severe disease:

- Oxygen saturation < 93% by pulse oximetry.
- Lower chest wall in-drawing.

RSV infection:

Detection of RSV by reverse transcription-quantitative real time polymerase chain reaction (RT-qPCR) in swab sample collected within 72 hours of first identification of a potential LRTI by the investigator/study staff during an active or passive surveillance study contact.

Start date of the LRTI case:

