11.2.1.4.5. Any LRTI (Nokes definition)

The subject will be defined as LRTI positive according to Nokes definition when he is presenting:

- history of cough or difficulty breathing,
- and at least one of the following:
 - Fast breathing, or
 - Indrawing, or
 - Low oxygen saturation (< 90%) by pulse oxymetry when accompanied by a clinical diagnosis of LRTI or bronchiolitis.

For derivation purposes we are characterizing 2 groups of items:

- Component A which gathers items used to derive history of cough and difficulty breathing,
- Component B which gathers Fast breathing, Indrawing, Low oxygen saturation (< 90%) by pulse oxymetry when accompanied by a clinical diagnostic of LRTI or bronchiolitis.

Component A:

The subject will be considered positive for Component A when one or several of the following items is reported in interview during the examination visit:

- Cough reported in interview during the examination visit or Dica (fields [EXAM_VS.SYMP_CAT]="Cough" and [EXAM_VS.SYMP_REP]="Y")
- And/or difficulty breathing as defined in section 11.2.2.1

Component B:

The subject will be considered positive for Component B when at least one of the following statements is reached:

- Increased Respiratory rate as defined in section 11.2.2.2
- **AND/OR** Any chest indrawing present at examination visit (fields [CLN_SIGN.SIGN_CAT]="Chest indrawing" and [CLN_SIGN.SIGN_YN]="Y").
- **AND/OR** Low oxygen saturation (< 90%) by pulse oxymetry (field [CLN_SGN2.BLSAT_V]) associated with clinical diagnostic of respiratory infection. (fields [CLN_DIAG.DIAG_YN]="Y")

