11.2.2.2. Increased respiratory rate

The subject will be considered to have increased respiratory rate if one of the following statement is reached:

- Respiratory rate (field [CLN_SGN2.RESPR_V])
- > 60/minute for subjects <2 months of age (fields [DEMOG.DOB_RAW] and [EXAM_VS2.ACTU_DT])
- > 50/minute for subjects 2-11 months of age(fields [DEMOG.DOB_RAW] and [EXAM_VS2.ACTU_DT])
- > 40/minute for subjects 12-24 months of age(fields [DEMOG.DOB_RAW] and [EXAM_VS2.ACTU_DT])

Please note that respiratory rate is measured during the examination visit.

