WHO RSV Severe LRTI (< 6 months of age)	RTI and $93\% \le SaO2 < 95\%$ and No increased respiratory rate and at least one symptom induced by difficulty breathing		
	RTI and 93% \leq SaO2 < 95% and increased respiratory rate and at least one symptom induced by difficulty breathing ²		
	RTI and SaO2 < 93% and no increased respiratory rate and no symptoms induced by difficulty breathing		
	RTI and SaO2 < 93% and increased respiratory rate and no symptoms induced by difficulty breathing		
	RTI and SaO2 < 93% and No increased respiratory rate and at least one symptom induced by difficulty breathing		
	RTI and SaO2 < 93% and increased respiratory rate and at least one symptom induced by difficulty breathing		

RTI = respiratory tract infection

SaO2 = Blood Oxygen Saturation

LRTI= Lower respiratory tract infection

N = total number of episodes

n/% = number / percentage of episodes in a given category

Increase respiratory rate: \geq 60/minute (< 2m of age); \geq 50/minute (2-11m of age); \geq 40/minute (12-24m of age)

Symptoms induced by difficulty breathing: Irritability/agitation, Lethargy/sleepiness, Severe chest in drawing,

Reduced/no vocalization, Apnoea > 20 sec, Cyanosis, Stop feeding well/dehydration

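### The SAP gives the Kenyan birth-cohort comparator the WHO/sponsor fast-breathing rule, including a 12-24 month limit that the protocol's definition lacks, and states the WHO cut-off inconsistently (≥ in two footnotes, > in the derivation)

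*SAP*

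**What the plan says.** **Comparator.** Protocol 4.1 gives its fast-breathing sign as "Fast breathing for age (≥ 60 breaths/minimum if the child is < 2 months old or ≥ 50 breaths/minimum" at 2-11 months. No figure is given from 12 months. Indrawing, or saturation below 90% (or inability to feed) with a clinical diagnosis, also qualifies. SAP 11.2.1.4.5 replaces the rate sign with "Increased Respiratory rate as defined in section 11.2.2.2". That section starts with "> 60/minute for subjects <2 months of age", continues with above 50 at 2-11 months, and ends with "> 40/minute for subjects 12-24 months of age".

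**WHO and sponsor definitions.** Protocol 4.1 is strict for WHO: "Fast breathing, (> 60 per minute in a child < 2 months of age, > 50 per minute in a child 2 to 11" months, and above 40 from 12 months. Protocol Table 4 is equally strict for the sponsor's definition, and protocol Table 3 lists rates up to and including 60, 50 and 40 as normal. The SAP derivations of both (11.2.1.4.1 and 11.2.1.4.3) call 11.2.2.2, which agrees. SAP Table 4 footnote 3, marked on the WHO rows, says "RR defined as ≥ 60/minute (< 2 months of age); ≥ 50/minute (2 to 11 months of age", and at least 40 at 12-24 months. The Template 29 footnote likewise puts ≥ before "60/minute (< 2m of age" and before its 50 and 40.

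**Exploratory definition.** SAP 11.2.1.6 gives no derivation for it and refers to Table 4. That row requires a raised rate, with no footnote marker visible in the text available.

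**Declared changes.** SAP section 9 lists many departures from the protocol, but no change to a respiratory-rate rule. It does say that incidence under the sponsor and Kenyan definitions is not computed.

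**The concern.** The second co-primary objective is to assess how the LRTI case definitions perform against each other. That requires each comparator to be the one the protocol names. If the SAP is programmed as written, the Kenyan comparator borrows the WHO rate rule in all three age bands. Below 12 months this removes a real boundary difference between the two definitions. From 12 months it adds a criterion that the protocol's text does not contain. The second change is the more serious, because it reaches every second-year child breathing faster than 40, not only those on a boundary. Templates 20 and 21 pool all ages, so the reader of the tables could not see it.

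The ≥/> conflict is a lesser matter. One endpoint, WHO RSV LRTI, has two written cut-offs in the same SAP. For the exploratory definition, the only operator that Table 4 spells out is the one that disagrees with the annex.

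**Working it through.** The plan states no figure to reproduce. The check sets the rules side by side, follows the reclassified children through the 2×2 table, and then illustrates scale on stated assumptions.

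**1. Is the rate criterion met?**

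| Age, rate | Protocol WHO/sponsor | SAP 11.2.2.2 | SAP Table 4 fn 3 / Template 29 | Protocol Kenyan |
|---|---|---|---|---|
| <2 m, 60 | no | no | yes | yes |
| <2 m, 61 | yes | yes | yes | yes |
| 2-11 m, 50 | no | no | yes | yes |
| 2-11 m, 51 | yes | yes | yes | yes |
| 12-23 m, 40 | no | no | yes | no |
| 12-23 m, 41 | yes | yes | yes | no |

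One breath below each cut-off, every rule says no. SAP 11.2.2.2 matches the protocol for WHO and sponsor on every row. It differs from the protocol's Kenyan rule at exactly 60, at exactly 50, and at every rate above 40 from 12 months.

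**2. Effect on agreement with WHO as reference**

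- *12-24 months, rate above 40, cough or difficulty breathing, no other comparator sign.* The child meets WHO component A and component B, so is a WHO case. Under the protocol's Kenyan rule the child is a comparator non-case (FN). Under the SAP the child is a comparator case (TP). Moving children from FN to TP raises TP/(TP+FN), TN/(TN+FN) and overall agreement, and cannot lower TP/(TP+FP). Specificity is unchanged.
- *Under 12 months, rate exactly 60 or 50, no other comparator sign.* The SAP drops the child as a comparator case. With saturation ≥95% the child is a WHO non-case and moves from FP to TN. With saturation <95% the child is a WHO case and moves from TP to FN. The net direction is not fixed.
- *Severe comparator status.* This needs indrawing, or low saturation with a diagnosis. Either already satisfies component B of the comparator, so the rate rule does not change who is severe.

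**3. The WHO boundary.** WHO LRTI needs component A (cough or difficulty breathing) plus saturation <95% or a raised rate. A child exactly on the cut-off therefore changes status between ≥ and > only if component A is met and saturation is ≥95%.

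**4. Scale, on assumptions not in the documents.** Take the rate at the examination visit as normal, with mean (SD) 50 (10), 42 (9) and 36 (8) in the three age bands. For recording step h and cut-off c:

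- P(at) = Φ((c + h/2 − mean)/SD) − Φ((c − h/2 − mean)/SD)
- P(above) = 1 − Φ((c + h/2 − mean)/SD)
- relative rise from > to ≥ = P(at)/P(above)

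| Cut-off | h = 1: at / above | Rise | h = 2: at / above | Rise |
|---|---|---|---|---|
| 60 | 0.024 / 0.147 | 16.5% | 0.048 / 0.136 | 35.7% |
| 50 | 0.030 / 0.173 | 17.3% | 0.060 / 0.159 | 37.6% |
| 40 | 0.044 / 0.287 | 15.3% | 0.088 / 0.266 | 33.0% |

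So the rise is 15-17% with single-breath recording and 33-38% with even-number recording. Letting the mean lie 0-10 below the cut-off and the SD run from 8 to 12 widens the range to about 7-54%. These are changes in the rate criterion alone.

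On the same assumptions, 27-29% of examined second-year children exceed 40. That is a ceiling on the share the added limit could make comparator cases, before removing those without cough or difficulty breathing and those with another comparator sign.

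**The case against.** The strongest reply is that the operative WHO and sponsor rule is already right. Table 4 is a summary that refers to 11.2.1 for detail. The derivations name database fields, call 11.2.2.2 and agree with the protocol, and Template 29 only subdivides cases already classified. A programmer would very likely use >. This stands, and it makes the footnotes a secondary point. It does not dispose of them: the SAP states no order of precedence, and the exploratory definition has only Table 4 to rely on.

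On the comparator, it is fair to say that its incidence is not computed, that its larger differences from WHO (indrawing, and saturation below 90% with a diagnosis) are kept, and that below 12 months only exact boundary values are touched. The protocol's silence from 12 months could also be called a gap rather than a deliberate omission. Even so, filling it with the WHO limit is an adaptation that should be declared. All analyses are descriptive, and protocol 9.10 allows deviations to be justified in the final report. That is an opportunity to disclose the change, not a reason to program an undeclared definition.

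Two stronger readings are tempting. A reader might infer that the main incidence result is at risk. WHO RSV LRTI is one of six listed incidence endpoints, and the first co-primary objective concerns RSV RTI with suspected lower-tract involvement, whose derivation uses no measured rate cut-off. A reader might also expect coarser counting, such as 15 seconds times four, to enlarge the boundary effect in every age band. But 50 is not a multiple of 4, so at 2-11 months the two operators would then select the same children.

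**Conclusion.** The comparator part is wrong as written. Following SAP 11.2.1.4.5 exactly would build the co-primary agreement tables for any RSV LRTI on a Kenyan definition that differs from protocol 4.1 in every age band, and section 9 does not say so. The 12-24 month addition matters most. It affects a whole range of rates, and against WHO its direction is fixed, towards better agreement. Comparator incidence is not computed and severe comparator status does not change.

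The footnote conflict is a genuine but smaller inconsistency. It is shown for the WHO rows; the text does not show the marker on the sponsor, Kenyan or exploratory rows. The exploratory operator is unclear.

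The size cannot be obtained from the documents, which give neither a rate distribution nor a counting method. The 15-17% and 33-38% figures depend wholly on the assumed distributions and describe the rate criterion. Reading them as changes in LRTI counts would be a mistake: low saturation also qualifies a child, so the effect on LRTI is smaller. No effect on kappa has been estimated.

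**What to change.** 1. In SAP 11.2.1.4.5, replace the cross-reference with a separate comparator variable that follows protocol 4.1: ≥60 under 2 months, ≥50 at 2-11 months, and no rate criterion from 12 months. Alternatively, keep the 12-24 month limit, declare it in section 9 as an adaptation, and also present the comparator's agreement tables for children under 12 months.
2. Change Table 4 footnote 3 and the Template 29 footnote to >60, >50 and >40, to match protocol 4.1 and SAP 11.2.2.2.
3. State the operator for the exploratory definition, in Table 4 or in a short annex entry.

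The cost is SAP wording, one derived variable and, under the alternative in step 1, an extra set of agreement tables. The rate and age are already recorded, so no new data are needed.
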